10.1.3 Follow up of (Serious) Adverse Events

Participants with SAEs (whether or not related to the study drug) will be monitored until resolution or until the event is considered chronic and/or stable by the investigator and/or other physician who has the responsibility for the subject's medical care. Treating physicians including general practitioners will be contacted for follow-up results. If necessary, participants will be contacted directly for follow-up. Follow-up SAE reports will be reported according to the same timelines as initial reports, as soon as new significant information becomes available. The outcome of AEs will be documented.

11. STATISTICAL METHODS

11.1 Hypothesis

Null hypothesis: Early administration of conestat alfa in addition to SOC is not associated with an improved clinical outcome in admitted COVID-19 patients as reflected by a lower score on the WHO Ordinal Scale on day 7 compared to SOC alone.

Alternative hypothesis: Early administration of conestat alfa in addition to SOC is associated with an improved clinical outcome in admitted COVID-19 patients as reflected by a lower score on the WHO Ordinal Scale on day 7 compared to SOC alone .

11.2 Determination of Sample Size

This is a pilot study investigating the efficacy and safety of conestat alfa in the prevention of clinical deterioration in a high-risk population with COVID-19.

There is no reliable information available on the clinical evolution of the population included in the trial. Therefore a precise quantitative pre-definition of the sample size of a population needed to obtain clinically significant primary endpoint is not possible at this point in time.

The assumptions which are proposed and the criteria to monitor and assess the primary endpoint are as follows:

The primary endpoint is a 7-point scale and the standard deviation σ can be expected as 1.5 points. A relevant effect δ is an advantage of at least 1 point. Then, the standardized difference is about $\delta/\sigma = 0.67$. For a fixed sample size design with a two-sided significance level of $\alpha = 0.05$ and a power of $1 - \beta = 0.80$, a sample size of $N = 2 \times 38$ is necessary. For a 2:1-randomization, a nonparametric analysis by the stratified logrank-test, and an adaptive group sequential analysis, the overall sample size is estimated as $120 = 80 + 40$.

Adaptive design:

Two interim analyses after 40 and 80 patients are planned according to the Pocock adjusted levels $\alpha_p = 0.0221$. Based on the results of an interim analysis the sample size can be adjusted (Lehmacher, Wassmer, 1999). There are no prespecified futility margins, but the DSMB can recommend stopping the study in the case of insufficient interim results.

The primary efficacy endpoint and the main secondary efficacy endpoints will be analyzed at latest at 14 days after start of treatment.

11.3 Statistical criteria of termination of trial

There are no prespecified futility margins, but the DSMB can recommend stopping the study in the case of insufficient interim results.

11.4 Planned Analyses

11.4.1 Datasets to be analysed, analysis populations

A review of the database will be conducted in a blinded manner shortly before the database will be locked, and any decisions made at that meeting (blinded Data Review Meeting) concerning the statistical analysis, e.g., additional outcomes and populations, pooling of sites for efficacy analysis, will be documented in the Statistical Analysis Plan (SAP).

Missing data for the primary endpoint will be imputed by means of the Last-observation-carried-forward (LOCF) method.

Safety Population: The Safety Population is defined as all patients who received at least one dose of conestat alfa. Statistical analyses will be based on the actual treatment the patient received.

Full Analysis Set/Intent-to-Treat Population: The FAS/ITT Population is defined as all patients who are randomly allocated to a study arm. Statistical analyses will be based on the treatment arm to which the patient was allocated.

For quantitative data, the number of patients with non-missing information, means, medians, standard

deviations and extremes will be determined. For qualitative data, absolute and relative frequencies will be calculated. Moreover, changes from baseline (V2, d0) will be calculated.

Per Protocol Population: The PP Population is defined as all patients in the FAS/ITT Population who complete the study and who do not have any major protocol violations, including the following:

- Patients who had major inclusion/exclusion criteria violations.

Sufficient compliance is expected because of IV administration of the IMP.

The PP Population will be determined by a blinded review in the Data Review Meeting (DRM) of the data prior to database lock.

The primary efficacy analysis will be based on the FAS/ITT Population in this superiority trial; an additional efficacy analysis will be performed on the PP Population. The Safety Population will be used for all safety analyses.

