5.4 Safety Outcomes

The study will evaluate the safety of conestat alfa in the setting of COVID-19 infections if added to SOC compared to SOC treatment only by measuring the incidence of adverse events up to 4 weeks inclusion.

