6. STUDY DESIGN

6.1 General study design and justification of design

This is an investigator-initiated, exploratory, randomized, parallel-group, open-label, multi-center, phase 2 clinical study in patients with confirmed COVID-19 infection and admitted to the hospital for treatment of SARS-CoV-2 infection to estimate the effect size of conestat alfa treatment in addition to standard of care compared to only standard of care on the proportion of patients surviving without requiring mechanical ventilation.

The study will recruit approximately 120 patients (80 patients in the intervention and 40 in the control arm) from several sites in Switzerland, Brazil and Mexico. Sites will be selected on the basis of estimated numbers of cases, the availability of a committed principal site investigator and research team, and the capacity to collect samples as per protocol.

Participants will be randomly assigned in a 2:1 ratio to conestat alfa treatment in addition to standard of care or only standard of care stratified by the site. Screening, informed consent and randomisation will happen as early as possible after admission to the hospital, usually within 72 hours after admission. Participants will receive intravenous conestat alfa or no additional treatment during a 72-hour period usually starting on the day of informed consent (=day 0). Both groups will continue to receive SOC treatment for COVID-19 infection. Blood samples will be collected before and during the 72-hour administration period. Follow-up will include the period until discharge and a telephone interview at four weeks (+/- one week) if participants are discharged earlier to assess potential adverse events.

Duration of participant's participation will be 4 weeks (+/- 5 days). Screening phase duration is up to 72 hours; treatment phase is a maximum of 72 hours, and follow-up period is 4 weeks after enrolment. At least three attempts will be made to contact the participant or his person of confidence at week 4 before the participant may be considered as lost to follow-up.

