8. STUDY INTERVENTION

8.1 Identity of Investigational Products (treatment / medical device)

8.1.1 Experimental Intervention (treatment)

Conestat alfa (Ruconest®) will be supplied by the production company Pharming Technologies, B.V., the Netherlands. Conestat alfa is a recombinant analogue of human C1INH for intravenous injection. The primary and secondary structures of the molecule and target protease selectivity are consistent with those of plasma-derived C1INH. Conestat alfa is purified from the milk of transgenic rabbits, and supplied as a sterile, preservative-free, white/off-white lyophilized powder for reconstitution for injection. Conestat alfa contains less than 0.002% of rabbit-related impurities. One international unit (U) of Conestat alfa activity is defined as the equivalent of C1INH activity present in 1 mL of pooled normal plasma. Each vial of Conestat alfa contains 2100 U of Conestat alfa, 937 mg of sucrose, 83.3 mg of sodium citrate dihydrate and 1.0 mg of citric acid monohydrate. After reconstitution with 14 mL of sterile water for injection, each vial of Conestat alfa contains 150 U of Conestat alfa per 1 mL in a 20 mM sodium citrate buffer with a pH of 6.8. Conestat does not contain preservatives and each vial is for single use only. After randomization, a study nurse will open the respective sealed boxes, will reconstitute the respective number of conestat alfa vials and prepare the study medication for the intervention group. The control group will not receive any study medication. Conestat alfa is for intravenous use only. The reconstituted solution is administered as a slow intravenous injection over approximately ten minutes. Recommended doses of Conestat alfa for the treatment of an acute angioedema attack are 50 U/kg if body weight <84kg and 4200 U if >84kg. A second dose may be administered at the same recommended dose level within a 24 hour period. The experimental intervention in our study does deviate from the Summary of Product characteristics regarding dosing of the licensed product. In addition, we will not use the product according to the licensed indication (FDA and EMA). A market batch will be used for the study.

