10.1.1 Definition and assessment of (serious) adverse events and other safety related events

An **Adverse Event (AE)** is any untoward medical occurrence in a patient or a clinical investigation participant administered a pharmaceutical product and which does not necessarily have a causal relationship with the study procedure. An AE can therefore be any unfavourable and unintended sign (including an abnormal laboratory finding), symptom, or disease temporally associated with the use of a medicinal (investigational) product, whether or not related to the medicinal (investigational) product. [ICH E6 1.2]. Any medical conditions present before signing the informed consent will be reported in the medical history. Any AEs that occur between screening and first treatment are considered as Non-Treatment Emergent Adverse Events (TEAE).

A **Serious Adverse Event (SAE)** is classified as any untoward medical occurrence that:

- results in death,
- is life-threatening,
- requires in-patient hospitalization or prolongation of existing hospitalisation,
- results in persistent or significant disability/incapacity, or
- is a congenital anomaly/birth defect.

In addition, important medical events that may not be immediately life-threatening or result in death, or require hospitalisation, but may jeopardise the patient or may require intervention to prevent one of the other outcomes listed above should also usually be considered serious. [ICH E2A]. An elective or pre-planned hospital admission will not be considered as a SAE. Note: an AE or adverse drug reaction is considered 'life-threatening' if, in view of either the Investigator or Sponsor, its occurrence places the patient at immediate risk of death. It does not include an event that, had it occurred in a more severe form, might have caused death.

SAEs should be followed until resolution or stabilisation. Participants with ongoing SAEs at study termination (including safety visit) will be further followed up until recovery or until stabilisation of the disease after termination.

Regardless of the assumed causal relationship, all AE volunteered by the trial subjects or observed by the investigator and/or his staff must be recorded on the AE forms. Records of AEs include patient data, description of the event, intensity, severity, relationship to the study drugs, temporal relation to the study drugs, action taken, description of outcome and documentation of the results of diagnostic and therapeutic measures.

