11.4.5 Safety analysis

The assessment of safety will be based mainly on the frequency of adverse events (AEs) that are treatment-emergent (TEAEs). Formal tests will not be conducted for differences in safety parameters between treatment groups.

The incidence of all treatment-emergent AEs will be tabulated after grouping by system organ class and preferred term. For each preferred term and summarized over each system organ class overall, the

table will present the absolute number and proportion (%) of patients in each treatment group in whom the event occurred. The incidence of all suspected-IMP-related AEs will be tabulated similarly. The incidence of all treatment-emergent AEs will also be tabulated by severity categories.

Safety will also be summarized with respect to vital signs as mean levels by visit and change from baseline. Abnormal observations on physical exams will be listed.

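### The Safety Population admits only patients dosed with conestat alfa, so the planned AE comparison with standard of care has no control group

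*Protocol*

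**What the plan says.** Section 11.4.1 defines the set: "The Safety Population is defined as all patients who received at least one dose of conestat alfa". The Statistical Considerations entry of the synopsis gives the same definition. Section 11.4.1 adds "Statistical analyses will be based on the actual treatment the patient received" and, on scope, "The Safety Population will be used for all safety analyses". It makes no exception.

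On exposure, Section 8.1.1 states "The control group will not receive any study medication", and Section 3.6 explains that there is no placebo group. On size, Section 6.1 states "The study will recruit approximately 120 patients (80 patients in the intervention and 40 in the control arm".

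The safety outcome in Section 5.4 is comparative: conestat alfa added to SOC is to be assessed "compared to SOC treatment only by measuring the incidence of adverse events up to 4 weeks inclusion". Section 11.4.5 bases safety mainly on treatment-emergent AEs, without formal tests, and says that the "table will present the absolute number and proportion (%) of patients in each treatment group in whom the event occurred".

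The boundary for treatment-emergent is in Section 10.1.1: "Any AEs that occur between screening and first treatment are considered as Non-Treatment Emergent Adverse Events (TEAE".

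**The concern.** One definition decides who is counted in all the safety tables, and it depends on a drug that the control arm never receives. Followed literally, the SOC column of each AE table has no patients in it. The definition of treatment-emergent makes this worse. Even if SOC patients were let into the set, the protocol does not say from when their events would count.

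The control column matters in this trial. Sections 1.6 and 10.1 say that complications are common in COVID-19 and that serious AEs are possible, and Section 2 expects about 20% of admitted patients to deteriorate despite supportive care. With that background, an AE or SAE rate in the conestat alfa arm alone says little about the drug. The randomised SOC arm is the benchmark inside the trial. The trial is also open-label, so the choice of control safety set and its time origin should not wait until event counts by arm are known.

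**Working it through.** This is a check of set membership, so the rules are set side by side and the patients counted.

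**Inputs**
- Planned arms: 80 conestat alfa, 40 SOC, 120 in total (Section 6.1). The split agrees with 2:1 allocation: 120 × 2/3 = 80 and 120 × 1/3 = 40.
- Entry rule for the Safety Population: at least one dose of conestat alfa (synopsis, Section 11.4.1).
- Study drug in the control arm: none (Section 8.1.1).
- Scope of the set: all safety analyses (Section 11.4.1).

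**Count as written, if every patient is treated as allocated**
- Conestat alfa arm in the set: 80 of 80.
- SOC arm in the set: 0 of 40.
- Safety Population: 80 + 0 = 80 of 120. The excluded share is 40/120 = 33%, which is the whole control arm.
- A control patient given conestat alfa by mistake would enter the set. Under the as-treated rule that patient would be counted under conestat alfa, so the SOC denominator stays at 0.

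**Set against the rest of the protocol**

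| Place | What it requires | Result under the definition |
|---|---|---|
| Section 5.4 | AE incidence against SOC | No SOC patients to count |
| Section 11.4.5 | Number and percentage in each treatment group | SOC percentage has denominator 0 |
| Section 11.4.1, as-treated rule | Grouping by treatment received | Only one group exists, so the rule has nothing to do |

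**Time origin**

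Section 10.1.1 classes events between screening and first treatment as not treatment-emergent. In the conestat alfa arm the boundary is the first administration. For SOC patients no first study treatment exists and no substitute date is named. Counting controls from consent and the conestat alfa arm from first dose would give the arms different windows. Correcting the population alone therefore leaves the main safety variable undefined in one arm.

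**What remains available**

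Section 9.2.4.1 follows participants in both arms for AEs for four weeks after enrolment. Section 5.3 lists mortality, ICU treatment, mechanical ventilation and acute kidney injury among the other outcomes of interest, and none of these is tied to the Safety Population.

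**Count after correction**

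80 + 40 = 120, if all patients allocated to conestat alfa are dosed. For an AE with the same incidence p in both arms, the 95% confidence half-width for the risk difference is 1.96 × √[p(1−p)(1/80 + 1/40)]. The protocol gives no AE rate, so p is assumed:
- p = 10%: 1.96 × √(0.09 × 0.0375) = 11.4 percentage points
- p = 20%: 1.96 × √(0.16 × 0.0375) = 15.2 percentage points

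These figures show how coarse the recovered comparison would be. The finding does not depend on them.

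**The case against.** The best defence is that the intent is plain. Sections 5.4 and 11.4.5 describe a two-arm comparison, and the as-treated sentence presupposes more than one group. Section 11.4.1 also lets the data review meeting add populations and record them in the SAP. This stands as evidence that the comparison can be recovered. It does not cure the text, because the protocol fixes the set twice and assigns it to all safety analyses. A SAP that counted SOC patients would depart from the protocol rather than fill a gap.

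A second defence concerns the time origin. The protocol calls SOC a control intervention, and Section 6.1 describes a 72-hour period for both arms that usually starts on day 0. A day-0 start for controls is therefore a possible reading. This stands in part: the fair criticism is that no start is stated for SOC patients, and this limb is weaker than the first.

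Third, no formal safety tests are planned and the trial is an exploratory pilot. That is true, but a descriptive percentage by group still needs a denominator.

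A reader might also infer that the DSMB loses the randomised safety comparison. The protocol does not support that. Section 1.6 has an independent statistician supply pertinent safety data under a separate charter, and nothing limits those data to the Section 11.4.1 set. Nor does it follow that harm cannot be compared with background at all, since death, ICU treatment, ventilation and kidney injury are assessed in both arms outside this set.

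**Conclusion.** The contradiction is real and nothing else in the protocol resolves it. As written, 0 of 40 planned SOC patients enter any AE or SAE table, although Sections 5.4 and 11.4.5 require them there. The start of the treatment-emergent period is also unstated for the SOC arm.

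The loss is limited to the pre-specified randomised AE and SAE comparison. The data are collected and the comparison can be restored. The primary and secondary efficacy analyses, the alpha levels and the sample size are unaffected. The count rests on the planned arm sizes and on controls receiving no conestat alfa. No assumption about AE rates is needed.

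**What to change.** 1. In the synopsis and Section 11.4.1, define the Safety Population as all patients randomised to SOC plus all patients who received at least one dose of conestat alfa, analysed by treatment received. An SOC patient given conestat alfa by error counts under conestat alfa.
2. List patients randomised to conestat alfa but never dosed separately, and keep them out of the SOC denominator. Sections 8.5 and 9.2.5 give no follow-up to patients withdrawn because they received no study medication. A rule that placed every undosed patient under SOC would add patients without AE follow-up and pull the control rate down.
3. In Sections 10.1.1 and 11.4.5, use one time origin for emergent AEs in both arms, randomisation (day 0), with the window running to week 4. Keep a table of events after first dose as an additional display for the conestat alfa arm.

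The cost is a change of wording in the synopsis and Sections 10.1.1, 11.4.1 and 11.4.5, with the SAP aligned, before database lock. No extra visits, data or patients are needed, because AEs are already recorded in both arms over the four weeks.

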11.4.2 Primary Analysis

The primary endpoint WHO 7-point outcome scale at day 7 will be analyzed by nonparametric logrank test stratified by its baseline values with two-sided α -level of 5 %.

Two adaptive interim analyses after 40 and 80 patients are planned according to the Pocock adjusted levels $\alpha_p = 0.0221$. The results of the sequential groups are combined by the inverse-normal-method (Lehmacher, Wassmer, 1999). There are no prespecified futility margins, but the DSMB can stop the study in the case of insufficient interim results.

Furthermore, 95% confidence intervals will be determined, and the results will be presented graphically by means of box-and-whisker plots.

The analyses will be carried out by the trial biostatistician.

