9.2 Assessments of outcomes

9.2.1 Assessment of primary outcome

For the analysis of the primary endpoint, illness severity will be assessed on each day after enrolment (worst status) with the use of the WHO Ordinal Scale for Clinical Improvement (score 0 will be omitted and score 6 and 7 will be combined) and the score on day 7 will be analysed stratified by its baseline value.

Patient State	Descriptor	Score
Uninfected	No clinical or virological evidence of infection	0
Ambulatory	No limitation of activities	1
	Limitation of activities	2
Hospitalized Mild disease	Hospitalized, no oxygen therapy	3
	Oxygen by mask or nasal prongs	4
Hospitalized Severe Disease	Non-invasive ventilation or high-flow oxygen	5
	Intubation and mechanical ventilation	6
	Ventilation + additional organ support – pressors, RRT, ECMO	7
Dead	Death	8

Figure 4: WHO ordinal scale for clinical improvement. For the current study, score 0 will be omitted, and score 6 and 7 will be combined.

The worst score on a given day (between 0:00 and 24:00 hours) will be used for the categorization

Patient State	Description	Score
---------------	-------------	-------

Outpatient	No limitation in activities	1
	Limitation in activities	2
Hospitalized Mild disease	No oxygen therapy	3
	Oxygen by mask or nasal prongs	4
Hospitalized Severe disease	Non-invasive ventilation or high-flow oxygen	5
	Intubation, mechanical ventilation +/- additional organ support	6
Death	Death	7

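### The primary endpoint, an uncensored ordinal score on one day, is tested with a logrank test whose result depends on a coding direction that the protocol does not state

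*Protocol*

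**What the plan says.** Protocol 11.4.2 fixes the primary test: "The primary endpoint WHO 7-point outcome scale at day 7 will be analyzed by nonparametric logrank test stratified by its baseline values", at a two-sided 5% level, with looks after 40 and 80 patients at the Pocock level 0.0221 and stage results combined by the inverse-normal method. The synopsis repeats the test. Section 11.2 names it again in the step to the total sample size: "a nonparametric analysis by the stratified logrank-test, and an adaptive group sequential analysis".

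The endpoint is a single score from 1 to 7, where 7 is death. According to 9.2.1, "the score on day 7 will be analysed stratified by its baseline value". Gaps are filled: "Missing data for the primary endpoint will be imputed by means of the Last-observation-carried-forward (LOCF) method" (11.4.1, repeated in 11.5). Section 11.1 defines benefit "as reflected by a lower score on the WHO Ordinal Scale on day 7 compared to SOC alone". No section says which end of the scale the logrank test treats as early.

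**The concern.** A logrank test compares times to an event when some times are censored. Here every patient has a value, death is itself a category, and the quantity is a severity grade. The test can still be computed by treating the score as if it were a time, but its weights then run from one end of the scale to the other. Reversing the scale changes the statistic, which does not happen with a Wilcoxon test.

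The choice of direction therefore decides whether the trial mainly looks for fewer ventilated or dead patients, or for better status after discharge. More than the final p-value depends on it. The same test drives the two interim efficacy looks and any sample-size change, and under 11.4.3 the secondary endpoints are tested only if the primary test is significant. Treatment is open-label and, under 6.2.2, DSMB members are not blinded, so a direction left open could be settled by people who know the results.

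**Working it through.** **1. The plan's own sample size.** Inputs from 11.2: an SD that "can be expected as 1.5 points", an effect that "is an advantage of at least 1 point", two-sided α = 0.05 and power 0.80.

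- Standardized difference 1/1.5 = 0.67. The t-test needs 36.3 per arm; divided by the Wilcoxon efficiency 0.955, this is 38.0. The stated 2 × 38 = 76 is reproduced.
- Step to 120: multiply by 9/8 for 2:1 allocation and by 1.167 for three Pocock looks (simulated), then divide by the efficiency of the test under a normal shift (logrank 0.816).
- From 76: 76 × 9/8 × 1.167 / 0.816 = 122. From 74 (t-test, 2 × 37): 119. With the Wilcoxon efficiency 0.955 in the last step: 105 and 102.

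The total of 120 fits a logrank allowance.

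**2. Dependence on coding, one data set.** Constructed scores 1 to 7, unstratified: treated (24, 24, 10, 10, 3, 6, 3), control (5, 9, 9, 9, 2, 4, 2). Go through the scores in coding order. At each score, d is the number of patients with that score and n the number with that score or a later one; n_T and n_C are the arms' shares of n. Then O − E = Σ(d_T − d·n_T/n), V = Σ d(n_T/n)(n_C/n)(n − d)/(n − 1), and z = (O − E)/√V.

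| Test | Numerator | Variance | \|z\| | p |
|---|---|---|---|---|
| Logrank, score 1 earliest | 7.16 | 17.44 | 1.71 | 0.087 |
| Logrank, score 7 earliest | −9.48 | 13.28 | 2.60 | 0.009 |
| Wilcoxon | 420 | 30,863 | 2.39 | 0.017 |

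The weight of a step between adjacent scores is d/n at the later of the two in coding order:

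- Score 1 earliest: the step between 1 and 2 counts 33/91 = 0.36, and between 6 and 7 it counts 5/5 = 1.00.
- Score 7 earliest: the step between 1 and 2 counts 29/29 = 1.00, and between 6 and 7 it counts 10/115 = 0.09.

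A second constructed set moves the other way: treated (20, 18, 20, 16, 3, 2, 1), control (9, 8, 8, 5, 3, 4, 3). It gives p = 0.053 (score 1 earliest), 0.36 (score 7 earliest) and 0.23 (Wilcoxon). Neither coding is always the favourable one.

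**3. The planned design under the planning assumption.** Simulation assumptions: three stages of 40 (27:13), two baseline strata, normal scores with SD 1.5 rounded and limited to 1 to 7, means 3 against 4 or 2.5 against 3.5, inverse-normal combination, level 0.0221 at each look.

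- Power: about 82% (score 1 earliest), 85% (score 7 earliest), 84% (stratified Wilcoxon).
- Opposite verdicts from the two logrank codings: about 11% of trials.
- With no effect, each test rejects in about 5%.

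**4. Other patterns of benefit.** Single look at 0.05, 80 against 40, one stratum. The protocol gives no outcome distribution, so these are assumed. Control: (10, 20, 25, 25, 5, 10, 5)%.

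| Treated distribution, % | Score 1 earliest | Score 7 earliest | Wilcoxon |
|---|---|---|---|
| Good end only: 30, 20, 15, 15, 5, 10, 5 | 17% | 64% | 44% |
| Severe end only: 10, 20, 33, 33, 2, 1.5, 0.5 | 43% | 14% | 21% |
| Common odds ratio 2.5 | 68% | 73% | 75% |

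**5. Direction chosen after seeing the data.** In the same single-look setting with no effect, the codings reject in 5.0% and 4.9% of trials and disagree in 5.1%. The chance that at least one rejects is (5.0 + 4.9 + 5.1)/2 = 7.5%.

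**The case against.** The scale is defined from 1 to 7, so a test run on the endpoint as written takes ascending order, and the SAP, which is not shown, may say so. Under the planning assumption either coding exceeds 80% power and loses or gains only 1 to 2 points against Wilcoxon. The example is constructed and unstratified, so on its own it does not show a changed verdict for the planned procedure. Ascending logrank is also stronger than Wilcoxon when benefit lies only at the severe end, and 4.2 and 6.1 stress avoiding ventilation.

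All of this stands, and it limits the point. It does not remove it. The choice of test is fixed in the protocol, not left to the SAP. The direction matters in about one trial in nine under the plan's own assumption. The protocol nowhere says that extra weight on the severe end is wanted.

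Three stronger readings are tempting, but the document does not support them:

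- **The sample size belongs to another test.** The base of 2 × 38 does match a Wilcoxon calculation, but 11.2 names the stratified logrank test in the step to 120, and 120 agrees with that allowance. At most, the factors are not shown.
- **The promised confidence interval has no estimand.** Section 11.4.2 does not tie the interval to the logrank statistic. Its target is simply unnamed, which an SAP can settle.
- **The test is invalid.** With the direction fixed in advance, its type I error is near 5%.

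**Conclusion.** The concern holds as a should-fix on the choice and direction of the primary test. The logrank test is poorly suited to an uncensored ordinal score. Its verdict depends on an unstated direction, with about 11% opposite verdicts under a one-point shift with SD 1.5. Its power against benefit mainly through discharge is low in the natural ascending coding: 17% against 44% for Wilcoxon in one assumed scenario.

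The 11% and the 82% to 85% power rest on rounded normal scores and an assumed split into baseline strata. The larger power gaps rest wholly on assumed outcome distributions and should be read as illustrations. The 7.5% error rate would apply only if the direction were chosen after the data were seen, and nothing in the protocol says that it would be.

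**What to change.** Before the first interim analysis, in the synopsis, 11.2 and 11.4.2, replace the logrank test for the primary endpoint with a Wilcoxon test stratified by baseline score (van Elteren), or the equivalent stratified proportional-odds score test. Compute it per stage and combine the stages by the inverse-normal method as already planned. Report a common odds ratio, or the probability of a better score, with its confidence interval. Keep the logrank test for the time-to-event endpoints.

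If the logrank test is kept, state in advance which end of the scale is early and why.

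The cost is an amendment of wording, with no change to data collection. The total of 120 need not rise, since the Wilcoxon allowance gives 102 to 105. The downside is less power than ascending logrank if the benefit lies only in the severe tail (21% against 43% in the assumed scenario).
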